## 4 STUDY DESIGN

### 4.1 OVERALL DESIGN

**Study Design:** This behavioral trial will use a two-arm randomized controlled design. Each of the 60-90 care partner participants will be randomized to an active “JITAI” arm (n=10-15 care partners of SCI, n=10-15 care partners of HD, n=10-15 care partners of HCT) or to a control arm (n=10-15 care partners of SCI, n=10-15 care partners of HD, n=10-15 care partners of HCT). The random allocation of participants to the treatment arm or control arm establishes the basis for testing the statistical significance or difference between the groups.

**Randomization:** Blocked randomization will be used to limit bias and achieve an equal distribution of participants to the control and treatment arms. A randomization list will be generated for each condition (SCI, HD, HCT) and the study statistician will oversee randomization. The participant will be randomized once he/she is deemed eligible and has provided informed consent (i.e. at enrollment prior to baseline data collection). The study coordinator/research assistant who consented the participant will use the appropriate condition’s randomization list to assign the participant to the correct study arm.

**Duration of Study Participation:** Study participation for both arms of the study (control and JITAI) involves a baseline assessment, followed by an approximate 10-day run-in period then a 3-month (90 day) home monitoring period (in which the intervention will be administered to the JITAI group). Thus, the total duration of the study is ~100 days.

**Study Sites:** This is a single-site study at the University of Michigan.

**Study Intervention:** The just in time adaptive intervention (JITAI) uses sensor data derived from the Fitbit® (e.g., accelerometer-based estimates of physical activity and sleep) and real-time self-report ratings (assessed once daily) of HRQOL (caregiver strain, depression, anxiety) to deliver personalized “pushes” to participants via a study specific app (CareQOL app). The personalized pushes will be delivered on ~50% of the days over the 3-month intervention period.

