### 6.3 CONCOMITANT THERAPY

There are no concomitant treatment or management strategy restrictions for this study. Information about current treatments (medications and non-medications) will be collected at baseline. Changes in treatments will be captured at the end of month 3 (~90 days) during the home monitoring period.

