## 7 STUDY INTERVENTION/EXPERIMENTAL MANIPULATION DISCONTINUATION AND PARTICIPANT DISCONTINUATION/WITHDRAWAL

### 7.1 PARTICIPANT DISCONTINUATION/WITHDRAWAL FROM THE STUDY

Participants are free to withdraw from participation in the study at any time upon request.

An investigator may discontinue a participant from the study for the following reasons:

- Lost-to-follow up; unable to contact participant (see **Section 7.2, Lost to Follow-Up**)
- Any event or medical condition/situation that occurs that would indicate that continued collection of follow-up study data would not be in the best interest of the participant or might require treatment that would confound the interpretation of the study
- The participant meets an exclusion criterion (either newly developed or not previously recognized) that precludes further study participation
- The participant is non-compliant with the study protocol

The reason for participant discontinuation or withdrawal from the study will be recorded. Participants who provide informed consent and are randomized but do not complete the 10-day run-in period will be replaced. Participants who withdraw or are discontinued before the end of the 3-month (~90 day) home monitoring period will be replaced.

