## 9.3 POPULATIONS FOR ANALYSES

The primary endpoint will examine survey responses on the feasibility and acceptability questionnaire that is designed to evaluate our intensive data collection protocol in the full sample (i.e., N=60 care partners). Secondary endpoints will include attrition and adherence estimates (again across the full sample). Exploratory analyses will be conducted to identify trends for an improvement in HRQOL scores (i.e., strain, depression, and anxiety) for care partners that are randomized to the intervention group. These analyses will also look for a trend for an improvement in the remaining HRQOL scores for care partners that are randomized to the intervention group, and will compare the JITAI group with the control group on all of the different HRQOL measures. Exploratory analyses may also compare important subgroups (e.g., caregiver groups that differ by diagnosis [SCI, HD or HCT], relationship type [parent vs. spousal caregivers], caregiver groups that differ by sex [male vs. female caregivers], caregiver groups that differ according to the functional status of the person with TBI (e.g., complicated mild vs. moderate vs. severe TBI or perceived functional status based on Mayo Portland Adaptability Index scores). Exploratory analyses will be an intention-to-treat approach where the participant will contribute data to the arm he/she was randomized to regardless of the amount of data contributed (i.e. the duration of participation).

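### Section 7.1 allows discontinuation and replacement of randomised participants who might need confounding treatment; this is in tension with 6.3, and Day 90 data can be lost for outcome-related reasons

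*Combined protocol and SAP*

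**What the plan says.** Section 7.1 lists reasons for stopping and introduces them with "An investigator may discontinue a participant from the study for the following reasons". One reason covers an event, condition or situation that makes further follow-up contrary to the participant's best interest, or that "might require treatment that would confound the interpretation of the study". No treatment is named. The section then states: "Participants who withdraw or are discontinued before the end of the 3-month (~90 day) home monitoring period will be replaced". The reason for each discontinuation is recorded.

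Section 4.1 places randomisation "at enrollment prior to baseline data collection", so everyone discontinued during home monitoring has already been randomised.

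Section 6.3 says: "There are no concomitant treatment or management strategy restrictions for this study". Treatments are recorded at baseline and changes at the end of month 3.

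Section 9.3 says: "Exploratory analyses will be an intention-to-treat approach where the participant will contribute data to the arm he/she was randomized to", and that this holds "regardless of the amount of data contributed (i.e. the duration of participation". Section 10.1.3 keeps the data of those who withdraw.

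The exploratory endpoints in Section 3 are changes from baseline to the end of the 90-day period in strain, depression and anxiety. Section 9.4.1 names a two-group t-test, or a nonparametric substitute, and no method for missing values. The primary questionnaire is given at Day 90 only (9.4.2).

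**The concern.** A treatment that 6.3 leaves unrestricted can, under 7.1, be a reason to end someone's participation, even if the need for it is only anticipated. In a trial whose exploratory outcomes are mood and strain, new treatment for low mood, anxiety or stress is an obvious candidate for treatment that would confound, and worsening is an obvious reason to need it. Day 90 values could then be missing because of the outcome itself.

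Section 9.2 says the study should supply a point estimate of the intervention effect for a larger trial, so a distorted estimate would be carried forward. Section 9.1 words the exploratory hypotheses as decreases within the JITAI arm. Losing people who worsen in that arm would flatter such a decrease whatever happens among controls.

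**Working it through.** **1. The plan's own figure.** Section 9.2 gives 60 participants. The arithmetic agrees: 3 groups × 20 = 60 and 2 arms × 30 = 60. No alpha, power or effect size is stated, so there is no power calculation to reproduce. Section 4.1 allows 60 to 90, that is up to 3 × 15 = 45 per arm.

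**2. The sections side by side.**
- *6.3 against 7.1.* One restricts no treatment and plans to record changes. The other allows removal for a treatment that might be needed. Changes are recorded only at month 3, so for a person removed earlier the treatment itself may never be systematically recorded.
- *9.3 against 7.1.* 9.3 assigns whatever data exist to the randomised arm. Discontinuation is from the study, so later surveys are not expected. Baseline, Day 30 and Day 60 data may remain, but a change to Day 90 cannot be computed and the t-test omits the person.
- *Primary endpoint.* The questionnaire exists only at Day 90. Section 9.3 describes the full sample as 60 and does not say whether, with replacement, this means everyone randomised or 60 people who finished.
- *Attrition.* Section 9.4.3 divides final-assessment completers by all who completed baseline. A discontinued person who completed baseline stays in that denominator.
- *Adherence.* Section 6.2 calculates the percentages only for participants not withdrawn or lost to follow-up, so a discontinued person can leave that denominator.

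**3. Illustrative shift in an arm mean.** The number removed (k) and how much worse they would have been (d) are assumptions. Shift = d × k / n.
- n = 30: 5 × 1/30 = 0.17 and 10 × 3/30 = 1.0 T points.
- n = 45: 5 × 1/45 = 0.11 and 10 × 3/45 = 0.67 T points.

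For scale, take the T-metric SD of 10 and assume a baseline-to-Day-90 correlation of 0.5. The SD of change is 10 × √(2 × (1 − 0.5)) = 10. The standard error of the between-arm difference with 30 per arm is 10 × √(2/30) = 2.58. The top of the n = 30 range is 1.0/2.58 = 0.39 standard errors.

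**4. Extreme bound.** Suppose those removed from one arm are exactly the share p with the worst change. The mean shift is SD of change × φ(z at 1 − p)/(1 − p), which with an SD of change of 10 gives 1.1, 2.0 and 3.5 points at p = 5%, 10% and 20%. At 10% (3 of 30) it runs from 1.5 (correlation 0.7) to 2.3 (correlation 0.3). If both arms lose people alike, the between-arm shift largely cancels, but the within-JITAI change still moves.

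**5. Effect of replacement on the primary percentage.** This covers all grounds for discontinuation together, with the share again assumed. To finish with 60 completers, 60/(1 − share) must be randomised: 64, 67 or 75 at 5%, 10% or 20%. An item endorsed by 48 of 60 (80%, the threshold in 9.1) is endorsed by 48/64 = 75%, 48/67 = 72% or 48/75 = 64% of all randomised.

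**The case against.** A reader might infer that 7.1 contradicts the intention-to-treat rule. It does not. That rule covers only the exploratory analyses and expressly allows for short participation, withdrawn participants' data are retained, and nothing in 7.1 removes anyone from an analysis set. What remains is practical: the rule cannot supply a Day 90 value that was not collected.

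A reader might also infer that replacement hides losses from the retention figure. The denominator in 9.4.3 rules that out. The point applies instead to the adherence percentages in 6.2 and to the undefined full sample.

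Nor does the plan direct removal of people who worsen, or say that unblinded staff decide. The clause is discretionary, is not tied to mood, and assigns the decision to an investigator whose blinding status is not stated.

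Opportunity is limited too. Treatment changes and adverse events are formally asked about only at month 3, when the final surveys are due, so earlier knowledge depends on spontaneous reports or routine contact. The illustrated shift is small against its standard error, and the outcomes are exploratory.

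Finally, 6.3 and 7.1 can be read together: one prohibits no therapy, the other gives discretion after an event. That reading is available, but the plan does not state it. These objections limit the size and wording of the concern. They do not fill the gap in Day 90 data.

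**Conclusion.** The concern holds in a limited form. Sections 6.3 and 7.1 are in tension, and following 7.1 as written can lose Day 90 values on a ground plausibly linked to the outcomes, with no missing-data method to compensate. How often the clause would be used is unknown. Under the stated assumptions the shift in an arm mean is about 0.2 to 1.0 T points with 30 per arm; the larger figures in step 4 need the worst changers in one arm to be exactly those removed.

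It would go too far to say that the effect estimate ceases to be a randomised comparison. The documents show a route to bias, not that bias will occur or that it would be large. The issue merits correction because correction is cheap.

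**What to change.** Reconcile 6.3, 7.1 and 9.3 so that they give one account of what follows when a participant may need other treatment. Which clinical rule applies is for the investigators. For the analysis, state that:

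- anyone discontinued on the confounding-treatment ground stays in the randomised arm and in the attrition and adherence denominators;
- all surveys collected from them are used, with a statement of how a missing Day 90 value is handled;
- the already scheduled Day 90 survey is still sought, unless consent is withdrawn or further data collection is judged not in the participant's best interest;
- replacements are additional to, not substitutes for, those discontinued, and the full sample is defined accordingly;
- such discontinuations and treatment changes are reported by arm.

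The cost is mostly wording. It adds a small amount of follow-up contact with people who would otherwise have left, and the feasibility and adherence figures may come out slightly less favourable.

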**Retention:** Given the intensive nature of this study, we expect that participants will miss some daily assessments and have times when they do not wear the Fitbit®; our retention plan is focused on minimizing these missed assessments and engaging participants throughout the study.

Retention will be facilitated by several strategies:

- App development will consider factors known to increase participant engagement including strategies to target engagement and minimize fatigue (easy to navigate platform, app tailoring based on Fitbit® sensor feedback, etc.). The app will also include a study team dashboard that we will use to monitor participant engagement.
- User guides and contact information for the study team (phone and email) will be supplied to participants and they will be encouraged to contact the study team with any questions or concerns.

- When enrolling participants, we will offer participants a choice of wristbands; they can select the wristband that is most comfortable and visually appealing to them. If they are not happy with their selection, we will provide an alternate wristband.
- Study staff will maintain regular contact with the study participants. All study participants will be contacted at least once during the study run-in period, at least once during the first week of the 3-month home monitoring period and at least once each month during the remaining months of the 3-month home monitoring period.
- Participants who do not complete any study assessments (e.g., uploading Fitbit® data or answering EMAs) for several days will receive a reminder from the study team.
- In case of lost equipment/equipment failure during the run-in and home monitoring periods, we will send replacements as supplies allow.

**Participant Incentives:** We will compensate participants for their time and inconvenience, as follows:

- Baseline assessment: Participants will receive \$20 for completing this assessment (\$20 total possible).
- Monthly HRQOL surveys during the home monitoring period: Participants will complete end of month surveys during the home monitoring period. Participants will receive \$10 for completing each end of month survey for months 1-3 (\$30 total possible).
- Daily EMA assessments and Fitbit® data during the 3-month home monitoring period: Participants will receive \$1 per day for each day that they have EMA and/or Fitbit® data during the three-month (90 day) home monitoring period (\$90 total possible).

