## 6.2 FIDELITY

For this study, the intervention will be administered via the CareQOL app. The study team will conduct training during the baseline visit with each participant which will include:

- Helping the participant download and register for the CareQOL and Fitbit® apps on their personal device
- Helping the participant set any relevant app settings (e.g., make sure alerts are turned on/off, privacy settings, etc.)
- Demonstrating the CareQOL app features to the participant (e.g., participant dashboard, etc.)

- Ensuring that the participant understands the importance of entering the daily ratings and wearing the Fitbit®
- Explaining the relationship between the daily ratings and Fitbit® data and the intervention prompts (JITAI group only)
- Demonstrating how to sync the Fitbit® (including using the Fitbit® app) and how to enter the daily ratings in the CareQOL app

During the 10-day run-in period between the baseline visit and the start of the intervention, study team members will assist participants to make sure that participants can:

- Successfully wear and sync the Fitbit®
- Successfully respond to the EMA prompts

Participants who are unable to successfully complete the run-in period will be terminated from the study and noted as a screen failure.

Training and training materials will be provided to all study team members. New study members will undergo training before the study is started. Training will be documented in the electronic regulatory binder.

Participant adherence to the protocol will be assessed throughout the study. Study staff will have access to the CareQOL app dashboard which can be used to monitor participant engagement and adherence with the app. Specifically, study staff will monitor:

- Adherence to EMA entry
- Adherence to Fitbit® use/syncing
- Adherence to completing the end of month surveys (~30, 60, 90 day)

Adherence will be calculated as a percentage for each of these areas for all participants who are not withdrawn or lost to follow-up.

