#### 9.4.3 ANALYSIS OF THE SECONDARY ENDPOINT(S)

##### Secondary Endpoints:

- Attrition (% of participants completing the final assessment—the assessment that is given at the end of month 3)
- Adherence (% missing data of total expected data for each person)

Attrition will be reported as the number of participants that complete the final assessment out of the total of number of study participants that completed the baseline assessment. In addition, the total number of days that participants completed EMA assessments, the monthly surveys, and the number of participants that complete the study will be calculated. Descriptive statistics will be calculated for missing data across the study period and by moment/day.

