**Protocol Deviations:**

This protocol uses the U-M IRBMED definition of a protocol deviation (<https://az.research.umich.edu/medschool/glossary/deviation>) which defines a protocol deviation as “an incident involving non-compliance with the protocol, but one that does not have a significant effect on the subject’s rights, safety or welfare, and/or on the integrity of the data. Deviations may result from the action of the participant, researcher or staff.”

We will follow the U-M IRBMED reporting guidance for protocol deviations found here <https://az.research.umich.edu/medschool/guidance/other-reportable-information-or-occurrence-orio>.

Reportable protocol deviations will be reported and tracked in the study REDCap database and will be discussed at investigator and project staff meetings.

The following events will not be reported as protocol deviations:

- A protocol deviation will not be reported for participants who skip/do not complete study survey questions or entire surveys (like end of month assessments or post-intervention surveys).

Participants can decline to answer any survey question for any reason. We expect in an intensive, long duration protocol like this that participants may miss some assessments.

- A protocol deviation will not be reported for out-of-window assessments. Use of this data will be assessed by the study investigators for each study analysis; some analyses may need tighter compliance to the assessment window while others will not.
- A protocol deviation will not be reported for participants who miss/do not complete the EMA assessments or do not wear/miss uploading Fitbit® data during the home-monitoring period. For example, we expect that there may be instances where participants are unable to complete the EMA assessments (for example, they are somewhere where it is inconvenient for them to answer) or forget to put on or sync the Fitbit®.
- A protocol deviation will not be reported for participants who decline the participant payment. It has been our experience that some research participants do not wish to receive payment for their participation in research studies.

Reportable protocol deviations will be reviewed at the project staff and investigator meetings.

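### Undefined non-compliance is a ground for discontinuation and replacement; with the Section 6.2 exclusion and a Day-90-only questionnaire, this can drop the least adherent participants from the adherence and primary results

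*Combined protocol and SAP*

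**What the plan says.** Section 7.1 lists the reasons for which an investigator may discontinue a participant. One is "The participant is non-compliant with the study protocol". No definition or threshold is given. The section then states: "Participants who withdraw or are discontinued before the end of the 3-month (~90 day) home monitoring period will be replaced". It treats the run-in the same way: "Participants who provide informed consent and are randomized but do not complete the 10-day run-in period will be replaced". Section 6.2 adds: "Participants who are unable to successfully complete the run-in period will be terminated from the study and noted as a screen failure". Under Section 4.1 randomisation takes place at enrolment, so these are randomised people.

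Three places bear on who is counted for adherence:

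- Section 6.2: "Adherence will be calculated as a percentage for each of these areas for all participants who are not withdrawn or lost to follow-up".
- Section 9.3: attrition and adherence are estimated across the full sample.
- Section 9.4.3: the endpoint is "Adherence (% missing data of total expected data for each person"), with no exclusion stated.

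The primary endpoint, the feasibility and acceptability questionnaire, is given at Day 90 only (Sections 8.1.5.3 and 9.4.2). Attrition in Section 9.4.3 is the number completing the final assessment divided by everyone who completed baseline.

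On missed data, Section 5.5 says "we expect that participants will miss some daily assessments and have times when they do not wear the Fitbit". Section 10.1.7 says "A protocol deviation will not be reported for participants who miss/do not complete the EMA assessments or do not wear/miss uploading Fitbit® data", and likewise exempts skipped surveys.

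**The concern.** Participants are asked mainly to answer the daily EMA items, wear and sync the Fitbit, and complete surveys. Not complying with the protocol is therefore, for the most part, a poor value on the adherence endpoint. A rule that permits removal on that ground, followed by an adherence calculation that leaves out withdrawn people, selects the analysed sample on the outcome.

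The primary endpoint is exposed by a different route. Someone discontinued before Day 90 is never asked the questions. If poor adherers would have agreed less often, agreement among the remaining respondents is too high.

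The plan sets criteria that these figures will be read against: at most 60% missing daily data and at least 80% agreement (Section 9.1). The results are meant to inform a larger trial (Section 9.2), so a favourable reading produced by selection would carry forward.

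**Working it through.** **No planned figure is in dispute.** Section 9.2 gives N = 60 from experience, without a power calculation. Its arithmetic is consistent: 3 × 20 = 2 × 30 = 60. The documents give no expected number of non-compliance discontinuations, so what follows is illustrative.

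**Illustration 1: adherence, with and without the Section 6.2 exclusion.** Assumed: 60 participants with mean EMA completion of 36%; eight of them, averaging 5%, are discontinued; eight replacements resemble those who remain.

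- All 60: 36% completed, 64% missing. Above the 60% limit.
- The eight excluded (Section 6.2): (60 × 0.36 − 8 × 0.05)/52 = 21.2/52 = 40.8% completed, 59.2% missing. Meets the limit. Adding eight replacements at 40.8% leaves it unchanged.
- Everyone counted (Sections 9.3 and 9.4.3): (60 × 0.36 + 8 × 0.4077)/68 = 24.86/68 = 36.6% completed, 63.4% missing. Above the limit.

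The same events give opposite readings depending on which section is followed.

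**Illustration 2: a range.** Let f be the share discontinued among all who start, a the missingness in those retained, and b the missingness in those discontinued. Full-sample missingness = (1 − f)a + fb. Section 9.1 expects at least 80% to complete, so f = 20% is the most that expectation allows. It corresponds to 60/0.80 = 75 baseline completers, 15 of them replaced, which lies within the 60 to 90 to be enrolled. Here all 15 are treated as excluded, whatever their reason for leaving.

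| f | a (reported under 6.2) | b = 80% | b = 90% | b = 100% |
|---|---|---|---|---|
| 10% | 55% | 57.5% | 58.5% | 59.5% |
| 20% | 50% | 56% | 58% | 60% |
| 20% | 55% | 60% | 62% | 64% |
| 20% | 60% | 64% | 66% | 68% |

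The last three columns are the full-sample figures. The share at which the full-sample figure reaches 60% is f = (0.60 − a)/(b − a). For a = 55% this is 20%, 14.3% and 11.1% at b = 80%, 90% and 100%. For a = 50% it is 33%, 25% and 20%. The verdict on adherence therefore changes only when retained participants are already fairly near the limit or the excluded share is substantial.

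**Primary agreement.** With 75 baseline completers and 60 finishers, 48 agreeing is 48/60 = 80% of finishers and 48/75 = 64% of baseline completers. The second figure is a lower bound that counts every missing response as not agreeing.

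**Attrition.** Under Section 9.4.3 the same case gives 60/75 = 80% completing. The 15 remain in the denominator.

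**The case against.** Discontinuation stops further data collection but does not by itself remove anyone from an analysis. Data from people who withdraw are retained (Section 10.1.3), Section 9.3 speaks of the full sample, and Section 9.4.3 uses each person's expected data. A reader might infer that Section 7.1 alone biases adherence. It does not: the exclusion comes from the last sentence of Section 6.2, and without it Illustration 1 stays above 60%. That part of the objection stands. It does not settle the matter, because Section 6.2 is still in the plan, retention does not define a denominator, and Section 9.3 equates the full sample with N = 60 without saying where replaced people go. Section 6.2 also says only withdrawn; that this covers investigator discontinuation is the natural reading but is not spelled out.

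A reader might also infer that Sections 5.5 and 10.1.7 flatly contradict Section 7.1. They do not. Section 5.5 expects some missed data, and its stated response to several days without data is a reminder. Section 10.1.7 is a reporting rule. Both suggest that routine gaps are not the target of Section 7.1, but neither limits it. That staff would act on the adherence dashboard is likewise inference; Section 6.2 says only that they monitor it.

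On size, the assumed values in Illustration 1 sit close to the limit. The one prior adherence figure in the documents (Section 2.2: 92% of participants giving data on at least 80% of days) is far from it, though it comes from 38 medical interns. Someone who has stopped responding might also skip the Day-90 questionnaire if left enrolled, so not all of the gap in primary agreement would be due to the clause.

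**Conclusion.** The point holds for adherence and for primary agreement. Read together, Section 7.1, the last sentence of Section 6.2 and the Day-90-only questionnaire allow the least adherent participants to drop out of both results, with bias towards a favourable reading. For adherence this depends on following Section 6.2 over Sections 9.3 and 9.4.3, and the plan does not say which governs. For the primary endpoint it assumes that those removed would agree less often than those who stay.

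It does not hold for attrition. A reader might infer that replacement inflates completion, but Section 9.4.3 keeps every baseline completer in the denominator, so discontinuation lowers it. What remains is narrower: a poor daily responder who might have finished becomes a non-completer by an investigator's decision. Whether run-in failures labelled as screen failures stay in that denominator is not stated.

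The size cannot be known from the documents. On the assumed values, reported missingness of 55% to 59.2% corresponds to full-sample values of about 60% to 64% when roughly 12% (8 of 68) to 20% are excluded. In a descriptive pilot with no formal test of these endpoints, this should be fixed but does not undermine the trial.

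**What to change.** - Replace the last sentence of Section 6.2 so that adherence is calculated for all randomised participants against total expected data over the full 90 days, including those withdrawn, discontinued or replaced. This brings it into agreement with Sections 9.3 and 9.4.3.
- Offer the Day-90 feasibility questionnaire to participants discontinued for non-compliance, and state whether a response then counts as completing the final assessment.
- Count replacements as additional participants, not as substitutes for those they follow.
- Report discontinuations and replacements by reason and arm (Section 7.1 already has reasons recorded), and show primary agreement also out of all baseline completers.
- Reconcile the non-compliance ground in Section 7.1 with Sections 5.5 and 10.1.7, which expect missed EMA, Fitbit and survey data. How that ground should read is for the investigators.

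The cost is a short amendment and one extra contact for each such participant. Reported adherence and agreement may be slightly less favourable. The questionnaire step has to be in place during follow-up, since responses never collected cannot be recovered in the analysis.
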